8.21 Strip Sign for Selected Laboratory Data

For selected laboratory test values that have been received with an operator sign as a part of the result (>, ≥, <, or ≤), a process to strip the operator sign will be applied and the resulting numeric values will be used for data analysis. The raw value with operator will remain as such on the CRF (or in the electronic record) and in the database.

The applicable impacted laboratory tests and applicable operator signs will be identified during the course of the study and study monitoring. For laboratory parameters not included in any statistical analyses, operator signs will not be stripped and the value will counted as missing.

8.22 United States Conventional Units and Standard International Units for Laboratory Data

Unless otherwise specified, all analyses of laboratory data (independently of being safety or efficacy) will be performed in both United States Conventional Units (US) and Standard International Units (SI). Conversion between US and SI, and vice versa, will be performed using the BMS standard conversion factors.

8.23 Laboratory evaluations

All laboratory evaluations performed by central laboratories and local laboratories that are included in the database will be included in summary tables and in the listings.

9 CONTENT OF REPORTS

The results of the study conducted by Protocol IM128-035 will be presented in a standard BMS CSR appendix. Key results and any unanticipated findings that are unusual for this study will be identified. A meeting for the initial dissemination of study results will be held after database locked. Attendees at this meeting will review all efficacy and safety summaries and listings and will identify key results that should be highlighted in the CSR.

APPENDIX 1 RELEVANT PROTOCOL DEVIATIONS

Number	Relevant Protocol Deviation Criteria	Exclusion Level
1	Randomized subjects who do not have moderate to severe primary Sjögren's syndrome, defined as Sjögren's syndrome in the absence of another autoimmune disease or rheumatologic condition) based on the 2015 ACR-EULAR Classification Criteria.	Complete exclusion
2	Randomized subjects without ESSDAI \geq 5, including disease activity (any score $>$ 0) in at least one of the following domains: Glandular, Articular, Hematological, Biological, Lymphadenopathy.	Complete exclusion
3	Randomized subjects without Positive anti-SS-A/Ro or anti-SS-B/La autoantibody.	Complete exclusion
4	Randomized subjects who received more than 10mg/day of prednisone (or prednisone equivalent) for at least 14 days prior to Day 1 (randomization).	Complete exclusion
5	Randomized subjects who did not receive at least 4 consecutive doses of Lulizumab or matching placebo.	Partial exclusion (Efficacy data after the 21th day of the interruption will be excluded)
6	Randomized subjects who did not receive BMS-986142 or matching placebo for at least 14 consecutive days.	Partial exclusion (Efficacy data after the 14th day of the interruption will be excluded)
7	Randomized subjects to placebo receiving active medication dose of Lulizumab for at least 4 doses and BMS-986142 for at least 14 doses.	Partial exclusion (Efficacy data from the first dose date of active medication will be excluded)
8	Randomized subjects receiving initiating or increasing the baseline dose (if already in such a medication) in any of the protocol specified list of restricted and prohibited treatments during double-blind treatment period.	Partial exclusion (Efficacy data from the first dose date of restricted or protocol medication will be excluded)
9	Randomized subjects less than 80% or more than 120% compliant with any of the double-blind treatment regimens.	Complete exclusion

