NOTE: combination products including acetaminophen and narcotic analgesics (eg, acetaminophen with codeine phosphate, acetaminophen with propoxyphene napsylate, acetaminophen with oxycodone HCl, acetaminophen with hydrocodone bitartrate, etc.) are allowed provided the acetaminophen component dosage is accounted for in the maximum of 2 g/day
 - Narcotic analgesics must not exceed 30 mg/day of morphine or its equivalent
 - Tramadol doses must be stable
 - Acetylsalicylic acid is allowed in low doses (eg, ≤ 100 mg/day) for cardiovascular prophylaxis

Immunosuppressives

The following medications are prohibited during the screening, dosing and follow-up periods:

- methotrexate
- cyclophosphamide
- leflunomide
- azathioprine
- cyclosporine
- tacrolimus
- MMF
- rituximab
- belimumab
- tocilizumab

- All investigational and approved biologic therapies (including but not limited to abatacept, etanercept, anakinra, infliximab, etc.)
- Use of any investigational drug other than study medication

Hormonal Contraceptives:

The use of hormonal contraceptives (oral, via implant/depot or via eluting IUD) are prohibited as a method of highly effective contraception due to safety concerns from transient liver function test elevations observed in the drug-drug interactions study (IM006032) with BMS-986142 and a combination oral contraceptive (ethinyl estradiol and the norethindrone acetate). In the study, a total of 10 of 16 subjects that were dosed with the oral contraceptive and BMS-986142 in combination had mild to moderate elevations of transaminases without an associated increase of total bilirubin. The majority of ALT elevations were < 3xULN. The maximum increase occurred in one subject with an ALT 5.8x ULN without accompanying total bilirubin elevation. Most subjects had no symptoms, however, 3 subjects had nausea, 2 subjects had vomiting and 1 had chills. All of the elevated transaminase levels returned to baseline. An evaluation of the cause of the transaminase elevation is ongoing, but no marked changes in the exposures of BMS-986142 or the components of the oral contraceptive were observed in a preliminary assessment of the data (i.e. no pharmacokinetic drug-drug interaction occurred during co-administration).

In addition, the use of oral or implantable estrogen-based hormone replacement therapy is also prohibited until additional drug interaction data becomes available. See Section 3.4.1.3.

[REDACTED]

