6.3 Populations for Analyses

- All Enrolled Subjects, defined as all subjects who sign an informed consent
- All Randomized Subjects, defined as all subjects who were randomized to a treatment group
- Modified Intent-to-Treat (MITT) Analysis Population: All randomized subjects who have received at least one dose of the study medication. Subjects will be grouped according to the treatment to which they were randomized by IVRS/IWRS at the start of the study
- As-Treated Analysis Population: All Subjects who have received at least one dose of study medication. Subjects will be grouped according to the treatment that they actually received as opposed to the treatment to which they were randomized. Subjects will be grouped on an as randomized basis unless the subject received the incorrect medication for the entire period of treatment. In that case, the subject will be analyzed in the treatment group associated with the incorrect medication he/she received
- Biomarker Analysis Population, defined as all subjects that receive any study medication and have at least 1 post-treatment biomarker measurement
- Pharmacokinetic Population, defined as all subjects who receive any study medication and have any available concentration-time data
- Immunogenicity Population, defined as all subjects who receive study drug and have at least 1 post treatment immunogenicity measurement

Analyses performed for all randomized subjects will be according to the as randomized groups, that is, subjects are categorized to the group to which they were assigned by the IVRS/IWRS. Efficacy and safety analyses will be performed using the MITT Analysis Population and the As Treated Analysis Population respectively.

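### Relevant deviation 7 never flags an active-arm subject given the wrong study treatment, and read literally it flags a placebo subject only if both active drugs were received

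*SAP*

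**What the plan says.** SAP Appendix 1 lists nine relevant deviations. Only number 7 concerns what was in the dose. It covers subjects randomized to placebo "receiving active medication dose of Lulizumab for at least 4 doses and BMS-986142 for at least 14 doses". The consequence is partial exclusion: "Efficacy data from the first dose date of active medication will be excluded".

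Four other criteria touch on dosing or medication:

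- Criterion 5 covers subjects who "did not receive at least 4 consecutive doses of Lulizumab or matching placebo".
- Criterion 6 covers subjects who "did not receive BMS-986142 or matching placebo for at least 14 consecutive days".
- Criterion 8 covers starting or increasing a restricted or prohibited treatment. The list behind it, in Protocol section 3.4.1.2, includes "Use of any investigational drug other than study medication".
- Criterion 9 covers subjects "less than 80% or more than 120% compliant with any of the double-blind treatment regimens".

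The list is used in two ways. Under SAP section 7.2, all relevant deviations are listed and summarized by treatment group, and nobody is removed from an analysis population. A per-protocol analysis is optional if at least 10% of all subjects in the efficacy population have one. Under SAP section 7.5.1, the primary analysis is repeated without the affected data if more than 10% of any treatment group has a deviation that leads to exclusion of efficacy data. SAP section 6.3 assigns efficacy to the MITT population, grouped as randomized.

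**The concern.** A per-protocol repeat is meant to show the treatment contrast without data from subjects who did not take what they were assigned. Criterion 7 is the only route by which a wrong-treatment subject leaves that analysis, and it has two weaknesses.

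The first is the word *and*. Taken literally, a placebo subject who took lulizumab alone, or BMS-986142 alone, for the whole 12 weeks is not a relevant deviation. The second is scope: the rule names only the placebo arm, so dosing errors in the two active arms are not covered on any reading.

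Three things are at stake: whether the by-arm deviation summary is complete, whether the counts against the 10% triggers are right, and whether the repeat analysis does what it is for. There is also a timing issue. Section 7.2 requires these deviations to be identified before database lock and unblinding, so the wording should be settled before any actual case makes the choice look selective.

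**Working it through.** **Do other criteria catch a crossover?** Criteria 5 and 6 are satisfied by active product or matching placebo alike, and their exclusion notes speak of an interruption, so they concern missed dosing. The prohibited item quoted from criterion 8's list exempts study medication. That list also bars biologic therapies in general, but lulizumab is itself study medication here and BMS-986142 is an oral kinase inhibitor, so this does not clearly help. Criterion 9 rests on SAP section 8.20, which counts tablets and injections whatever they contain.

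**What does criterion 7 flag?** Apply it to full-course errors (12 injections, or 84 tablet days):

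| Error | Literal *and* | Either drug at its own threshold, placebo arm only | Any arm, non-assigned active drug | Adding placebo in place of active |
|---|---|---|---|---|
| Placebo given both drugs | yes | yes | yes | yes |
| Placebo given lulizumab only | no | yes | yes | yes |
| Placebo given BMS-986142 only | no | yes | yes | yes |
| Lulizumab arm given BMS-986142 instead | no | no | yes | yes |
| Lulizumab arm given BMS-986142 on top | no | no | yes | yes |
| BMS-986142 arm given lulizumab instead | no | no | yes | yes |
| BMS-986142 arm given lulizumab on top | no | no | yes | yes |
| Lulizumab arm given only placebo | no | no | no | yes |
| BMS-986142 arm given only placebo | no | no | no | yes |
| Flagged | 1 of 9 | 3 of 9 | 7 of 9 | 9 of 9 |

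**Size.** Inputs from Protocol section 8.1: 25 per arm, difference 3 points, SD 3.2, two-sided 0.05. The plan's own figure reproduces: noncentrality (3/3.2) × √(25/2) = 3.31 on 48 degrees of freedom gives 90.1% power, against a stated value of about 90%.

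The documents give no crossover rate, so let *k* of 25 placebo subjects be retained crossovers. Assume that each has the full 3-point effect and that the SD stays at 3.2. The expected difference is 3 × (1 − *k*/25).

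| *k* | Expected difference | Power, retained | Power, excluded (difference 3) |
|---|---|---|---|
| 1 | 2.88 | 87.7% | 89.5% |
| 2 | 2.76 | 84.8% | 88.8% |
| 3 | 2.64 | 81.5% | 88.1% |
| 5 | 2.40 | 73.8% | 86.3% |

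Each subject therefore costs 3/25 = 0.12 points. The standard error of the difference is 3.2 × √(2/25) = 0.905, so 0.12 is about 0.13 standard errors. The same arithmetic holds for *k* active-arm subjects given only placebo, but for that arm's contrast alone; a contaminated placebo subject affects both contrasts. At the maximum of 40 per arm the figure is 3/40 = 0.075.

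**Triggers.** At 25 per arm, 2 subjects are 8% and 3 are 12%. One uncounted crossover can therefore decide whether the section 7.5.1 repeat is run.

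**The case against.** The strongest objection is that *and* need not mean both drugs in one subject. No regimen in SAP section 6.2 combines the two active drugs. Criteria 5 and 6, just above, give each drug its own row with the same numbers, 4 and 14. Criterion 7 can be read as placebo subjects who took lulizumab at its threshold together with those who took BMS-986142 at its threshold. That reading is plausible, so a reader should not conclude that the SAP certainly demands both drugs. It repairs only the placebo rows, however, and the SAP does not state it.

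One might also read criteria 5 and 6 as referring to whichever product was assigned. That would catch some substitutions in the active arms, but the words accept either product and the notes describe an interruption.

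A reader might infer that every missed crossover pulls the active-placebo difference toward zero. The documents do not support that. The interim calculation in SAP section 7.11 assumes equal change in both active arms; on that assumption, one active drug given in place of the other leaves the placebo contrast unchanged. A second active drug given on top could widen it.

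A reader might also look to the as-treated rule, which keeps subjects as randomized "unless the subject received the incorrect medication for the entire period of treatment". SAP section 6.3 uses that population for safety only, so it was never the means of handling crossovers in efficacy and its narrowness is not a fault here.

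Finally, the affected analysis is a conditional sensitivity repeat. One placebo subject of 25 is 4% and would not trigger it alone. This stands, and it limits the importance of the point.

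**Conclusion.** The gap is real and small. On any reading, criterion 7 misses active-arm subjects who received the other active drug or only placebo; read literally, it also misses placebo subjects who received just one active drug. No other criterion, as worded, flags them. They are absent from the relevant-deviation summary and the 10% counts, and their efficacy data stay in the per-protocol repeat if it is run.

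It would be wrong to infer that the primary result is at risk: the MITT analysis keeps everyone as randomized by design.

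For placebo contamination, or an active-arm subject given only placebo, the dilution is at most about 0.12 points per subject at 25 per arm. That bound assumes the full planned effect at Week 12, whereas the thresholds of 4 injections or 14 tablet doses fall well short of a full course. Active-to-active crossovers blur which drug produced the effect, with no fixed direction of bias. Such events should be rare, and the power figures above are illustrations only. This is a desirable clarification, not a threat to the trial's conclusions.

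**What to change.** Reword criterion 7 to cover a randomized subject in any arm who either

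- received an active study drug not assigned to them (lulizumab for at least 4 doses *or* BMS-986142 for at least 14 doses), or
- was assigned an active drug and received placebo in its place for the same number of doses.

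Exclude efficacy data from the first incorrect dose. This keeps the SAP's own thresholds and its partial-exclusion approach. The cost is one or two sentences in the SAP before unblinding, with no change to trial conduct or data collection.

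Criterion 9 needs separate attention when Appendix 1 is opened. SAP section 8.20 computes compliance on two tablets a day, while Protocol section 4.5 describes three, so a fully adherent subject comes out at 3/2 = 150%, above the 120% limit. The two passages must be reconciled. This does not close the present gap, because applied literally it would remove every adherent subject and would not identify crossovers.

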3 INVESTIGATIONAL PLAN

3.1 Study Design and Duration

This is a 12-week randomized, double-blind, placebo-controlled, parallel group study with adaptive design features based on an interim analysis (IA). The study will initially have a 28-day screening period followed by up to 12 weeks of double-blind treatment with either lulizumab, BMS-986142, or a matching placebo.

Screening period:

The standard duration of the Screening Period is up to 28 days (4 weeks), with up to two Screening Visits allowed for subjects who require adjustment of oral corticosteroids or who are taking HCQ. Subjects who are on oral corticosteroids at a dose higher than 10 mg/day will require a taper at the beginning of the Screening Period to a stable dose of no more than 10 mg/day of prednisone (or equivalent) for least 14 days prior to dosing (Day -14), and will need to be reevaluated prior to randomization (Day 1). Subjects who are taking HCQ at screening who meet the study criteria will be required to return for a second visit during the screening period to collect baseline HCQ PK samples as described in [Section 5.5](#) (these subjects should bring their daily dose of HCQ to the clinical site to be administered at the site). Should more time be needed, the duration of the Screening Period may be extended up to another week (total of 35 days or 5 weeks) depending on dose stabilization, technical issues, or subject scheduling. Study procedures will occur as specified in [Table 5.1-1](#).

Double-blind treatment period:

Upon meeting the Inclusion/Exclusion criteria, approximately 75 subjects with moderate to severe pSS will be equally randomized to 1 of 3 treatment arms (lulizumab, BMS-986142, or matching placebos) for up to 12 weeks of treatment, followed by a 6 week follow-up period after completion of treatment. During this period, the dose of oral corticosteroids, hydroxychloroquine, pilocarpine, cevimeline, cyclosporine eye drops, lifitegrast, autologous serum eye drops, oral and ocular lubricants and/or NSAIDs should remain stable. No additional immunosuppressive medications may be started unless indicated for the treatment of adverse

events. Analgesics are permitted with certain restrictions (see [Section 3.4.1.2](#)). Study procedures will occur as specified in [Table 5.1-2](#), [Table 5.5-1](#), and [Table 5.6-1](#).

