3.4.1.2 Restricted/Prohibited Treatments During Double-Blind Treatment Period

All restrictions during the double-blind period only apply to the management of symptoms for pSS.

For concomitant treatments for other conditions, see [Section 3.4.1.3](#). Some of the drugs used for other conditions may result in drug interactions and may be prohibited or restricted. Any medication initiated during the treatment period should be discussed with the BMS Medical Monitor.

Hydroxychloroquine (Plaquenil®)

All subjects who enter the screening period on hydroxychloroquine must remain on a stable dose of no more than 400 mg daily from the time of signing the informed consent for the duration of the study. New initiation of hydroxychloroquine, a daily dose > 400 mg/day, or a change in the dose of hydroxychloroquine is not permitted during the screening or dosing periods. The use of other antimalarials is not permitted.

Steroids

All subjects taking oral prednisone or its equivalent during screening must remain at a dose ≤ 10 mg/day for the entirety of the dosing period. Intra-articular, intramuscular (IM) or intravenous (IV) corticosteroid injections, or initiation of topical corticosteroid eye preparations are not permitted during the screening or dosing periods unless required for treatment of adverse events in consultation with the BMS Medical Monitor.

Ocular and Oral Lubricants

Subjects who enter the screening period on a stable dose of pilocarpine, cevimeline (Evoxac®), topical corticosteroid eye preparations, cyclosporine eye drops (Restasis®), lifitegrast (Xiidra®), or autologous serum eye drops are permitted to remain on these medications during the screening and dosing period, but must hold the dose(s) for at least 12 hours prior to any study visit until all study assessments are completed. These medications may not be initiated during the screening or dosing period. Artificial tears and saliva are permitted but must be held on the day of a study visit until all study assessments are completed.

Analgesics and NSAIDs

- NSAIDs doses should remain stable with the exception of decreases being permitted due to related adverse events, such as gastric toxicity.
- Analgesics
 - Acetaminophen (paracetamol) maximal dose 2 g/day

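### SAP Appendix 1 criterion 8 does not match the protocol's concomitant-treatment rules, so the conditional per-protocol repeat (not the primary analysis) would exclude the wrong data

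*SAP*

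**What the plan says.** SAP Appendix 1 lists nine relevant protocol deviations. Within the double-blind phase, criterion 8 covers randomized subjects "initiating or increasing the baseline dose (if already in such a medication) in any of the protocol specified list of restricted and prohibited treatments". Its exclusion level is partial, and the rule reads "Efficacy data from the first dose date of restricted or protocol medication will be excluded".

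The list it points to matches the title of protocol 3.4.1.2, "Restricted/Prohibited Treatments During Double-Blind Treatment Period". That section mixes several kinds of rule:

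- Outright prohibition, for the bulleted immunosuppressives and biologics.
- Stability. For hydroxychloroquine, "a change in the dose of hydroxychloroquine is not permitted during the screening or dosing periods". NSAIDs and tramadol are also to stay stable, with NSAID decreases allowed for related adverse events.
- Use up to a limit: "Acetaminophen (paracetamol) maximal dose 2 g/day" and "Narcotic analgesics must not exceed 30 mg/day of morphine or its equivalent".
- Permitted use with timing conditions: "Artificial tears and saliva are permitted but must be held on the day of a study visit".

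Section 3.4.1.2 opens by confining its double-blind restrictions to the management of pSS symptoms. Protocol 3.1 says "Analgesics are permitted with certain restrictions" and refers to 3.4.1.2 for them.

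SAP 7.2 keeps flagged subjects in every analysis population. It applies Appendix 1 only in a per-protocol analysis, and it requires deviations to be identified before lock and unblinding. SAP 7.5.1 repeats the primary analysis without the excluded data if more than 10% of any treatment group has such a deviation.

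**The concern.** Appendix 1 is the rule a programmer will follow to build the per-protocol data set. If criterion 8 does not reproduce the protocol's concomitant-treatment rules, that data set drops some data from subjects who complied and keeps some data from subjects who did not. It also drops more than intended from subjects whose background dose was raised. The same flags count toward the 10% trigger, so the decision to run the repeat inherits the error. This is the criterion through which the supportive analysis deals with concomitant treatment. Hydroxychloroquine and oral corticosteroid use are the two stratification factors (protocol 4.4), so the design itself treats background therapy as important.

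**Working it through.** This is mainly a comparison of texts, followed by a short calculation of scale.

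**1. Cut date.** Criterion 8 expressly includes subjects already taking the drug at baseline. Protocol 3.3.2, exclusion 5(e), rules out hydroxychloroquine started within 8 weeks of enrollment, so the first dose of background hydroxychloroquine is at least 56 days before enrollment and hence before Day 1. Table 5.1-2 schedules six post-baseline ESSDAI assessments in the treatment period: Days 15, 29, 43, 57, 71 and 85. Take an invented case with a dose increase on Day 50:

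| Cut dated from | Post-baseline ESSDAI visits kept |
|---|---|
| First dose of the medication (literal text) | 0 of 6 |
| The increase on Day 50 | 3 of 6 (Days 15, 29, 43) |

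Week 12 is lost either way. The difference is whether the subject contributes earlier visits to the repeated-measures model or nothing at all, and the row is labelled partial. Criteria 5 and 6 date their cuts from the interruption. Criterion 7 uses nearly the same first-dose wording, but there it works, because active study drug starts only after randomization.

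**2. Direction of change.**

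| Event on study | Protocol 3.4.1.2 | Criterion 8 |
|---|---|---|
| Hydroxychloroquine started or increased | Barred | Flagged |
| Hydroxychloroquine decreased or stopped | Barred as a dose change | Not flagged |
| NSAID decreased for a related adverse event | Allowed | Not flagged |
| NSAID decreased for another reason | Not within the exception | Not flagged |

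Hydroxychloroquine is the clear case.

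**3. Permitted use.**

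| Started for pSS symptoms | Protocol 3.4.1.2 | Criterion 8, read literally |
|---|---|---|
| Acetaminophen at or below 2 g/day | Within limit | Flagged; later efficacy data cut, including Week 12 |
| Narcotic analgesic at or below 30 mg/day morphine equivalent | Within limit | Same |

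The criterion states no dose limit, no symptom scope and no exception for allowed use. SAP 7.4.7 plans to tabulate concomitant narcotic analgesics, so such use is foreseen.

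**4. Scale.** The documents give no deviation rates; every rate below is an assumption, used for illustration only.

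*Trigger.* In one arm, 10% of 25 is 2.5, so more than 10% means 3 subjects. With flag probability p per subject, a = P(Binomial(25, p) ≥ 3), and the chance that at least one of three arms triggers is 1 − (1 − a)³:

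- p = 5%: 33%
- p = 10%: 85%
- p = 20%: 99.9%

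SAP 7.2 states the trigger differently, as at least 10% of all subjects. That is 8 of 75 (10% is 7.5), and the corresponding chances are 3.4%, 48% and 99.0%.

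*Precision of the repeat.* Protocol 8.1 states about 90% power for 25 per arm, a 3-point difference, SD 3.2 and two-sided α of 0.05. The noncentral t distribution, with noncentrality 3 / (3.2 × √(2/25)), gives 90.1%, so the stated figure is reproduced. If 10%, 20% or 30% of each arm lost Week 12 data (n = 22, 20 or 17, rounded down), a t-test on those remaining has 85.9%, 82.4% or 75.5% power. This is a simplification, because the planned model also uses earlier visits.

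**The case against.** The best defence is that criterion 8 should be read in context. Appendix 1 lists protocol deviations, so use within a protocol limit is not one. The list could be taken as the bulleted immunosuppressives alone. The word partial, and the parallel with criterion 7, suggest the cut was meant to fall on the first offending dose. Restricting exclusion to added or increased therapy is a defensible choice, and SAP 7.4.6 summarizes corticosteroid dose over time by arm.

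The intent may well be as described, but the text does not state it. The bulleted drugs are prohibited outright, so the words about restricted treatments and raising a baseline dose have little to apply to if the list stops there. The steroid summary does not cover hydroxychloroquine decreases.

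Several stronger inferences are tempting and are not supported:

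- That the primary result loses data. SAP 7.2 keeps flagged subjects in all analysis populations.
- That acetaminophen for an ordinary headache is clearly caught. Section 3.4.1.2 limits its restrictions to pSS symptoms and sends other conditions to 3.4.1.3, which is not available in the public text.
- That starting or increasing a lubricant is plainly compliant. Section 3.1 says lubricant doses should remain stable, while 3.4.1.2 permits artificial tears and saliva.
- That the reference to protocol medication means study drug. It looks like a slip for prohibited.
- That permitted use alone will meet the trigger. No rate in the documents supports this.

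**Conclusion.** The point holds as a mismatch between SAP Appendix 1 criterion 8 and protocol 3.1 and 3.4.1.2, confined to the conditional per-protocol repeat and the count toward its trigger. The cut-date fault and the missing hydroxychloroquine decreases follow directly from the wording. The flagging of permitted analgesics also rests on reading the named list as the whole of 3.4.1.2, which its title and the cross-reference in 3.1 support. The size cannot be fixed from the documents. What can be said is that three flagged subjects in one arm of 25 suffice under SAP 7.5.1, so a few wrong flags could decide whether the repeat is run. The matter should be corrected before lock, but it does not threaten the primary MITT analysis.

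**What to change.** Before database lock and unblinding, restate criterion 8 as a departure from the protocol's own rules:

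- Flag receipt of a treatment the protocol prohibits, exceeding a limit it states, or a start, increase, decrease or stop that 3.1 and 3.4.1.2 do not allow.
- Keep the pSS-symptom scope and the NSAID adverse-event exception.
- State that use within protocol limits is not a deviation.
- Exclude efficacy data from the date of the deviating start, excess or dose change, and correct the reference to protocol medication.

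Reconcile the protocol first. Section 3.1 and section 3.4.1.2 differ on lubricants (stable dose against permitted use) and on oral corticosteroids (stable dose against a ceiling of 10 mg/day). Which rule is right is for the sponsor; none is proposed here. The two versions of the 10% trigger in SAP 7.2 and 7.5.1 should be aligned at the same time.

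The cost is SAP wording and deviation programming. SAP 8.5 confirms that start and stop dates of non-study medications are collected. The team should check that dose and indication are also recorded well enough to apply the limits and the symptom scope, since the available text does not show this for every drug.
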